2.2 Analysis sets

The following analysis sets will be used in this study:

The **Enrolled Set** will include all patients, who provided informed consent.

The **Randomized Set** will consist of all patients, who were randomized into this study at Baseline. Mis-randomized patients will not be included in this analysis set.

[figure not shown]
The **Safety Set for Treatment Period 1 (SAF-TP1)** will consist of all patients, who received at least 1 dose of study treatment during this treatment period. Data will be analyzed according to the treatment actually received.

The **Safety Set for Treatment Period 2 (SAF-TP2)** will consist of all patients, who received at least 1 dose of study treatment during this treatment period. Data will be analyzed according to the treatment actually received.

The **Safety set (SAF)** will consist of all patients, who received at least one dose of study treatment. To analyze entire study period safety assessments, this dataset will be used.

The **Full Analysis Set for Treatment Period 1 (FAS-TP1)** will consist of all patients, who were randomized into this study at Baseline and received at least 1 dose of study treatment during this treatment period. Data will be analyzed according to the treatment assigned at randomization.

The **Full Analysis Set for Treatment Period 2 (FAS-TP2)** will consist of all patients, who were re-randomized or re-assigned at Visit 7 (Week 8) and received at least 1 dose of study treatment during this treatment period. Data will be analyzed according to the treatment assigned at randomization.

2.3 Patient disposition, demographics and other baseline characteristics

Summary statistics will be presented for continuous demographic and baseline characteristics for each treatment group and for all patients in the randomized set. The number and percentage of patients in each category will be presented for categorical variables for each treatment group and for all patients.

2.3.1 Patient disposition

The number and percentage of patients screened will be presented. In addition, the reasons for screen failures will be provided.

The number and percentage of patients in the randomized set, who enrolled, and who completed the treatment period and who discontinued the study prematurely (including the primary reason for discontinuation), will be presented at the end of each treatment period (Week 8 and Week 24), if appropriate, for each treatment group and all patients.

2.3.2 Patient demographic and other baseline characteristics

The following demographic and baseline variables, if collected, will be summarized:

Continuous variables:

- Age (which is derived from date/year of birth and the screening assessment date)
- Height
- Weight
- Body mass index (BMI) = (body weight in kilograms) / (height in meters)²
- For BMI, height and body weight used is the last value prior to randomization. If there is no weight recorded prior to taking of study drug, BMI will be missing.

Categorical variables:

- Age categories (<=30, >30-<55 and >=55)
- Sex
- Race
- Ethnicity
- Source of patient referral

Baseline disease characteristics will also be summarized for the following variables:

- History of axSpA including time (months) since first diagnosis of axSpA, time since first signs and symptoms, previous treatments of axSpA and reasons for discontinuation of these treatments.
- Smoking status at baseline
- HLA-B27 status [REDACTED]
- Spinal pain assessment on NRS, BASDAI, PASS, ASDAS, Patient's global assessment of disease activity, FACIT-Fatigue[®] and ASAS health index.

Unless otherwise specified, summary statistics will be presented for continuous variables for each treatment group and for all patients (total) in the randomized set. The number and percentage of patients in each category will be presented for categorical variables for each treatment group and all patients (total) in the randomized set.

Baseline disease characteristics QuantiFERON TB-Gold test and electrocardiogram related results will be listed only.

2.3.3 Medical history

Relevant medical history and current medical conditions will be summarized by system organ classes (SOC) and preferred terms (PT) of the latest version of MedDRA dictionary. Other relevant baseline information will be listed and summarized using descriptive statistics, as appropriate.

2.4 Treatments (study treatment, rescue medication, concomitant therapies, compliance)

2.4.1 Study treatment / compliance

Study Treatment

The summaries by treatment will be performed by the actual treatment received (as follows) for each treatment period.

Treatment group for period I:

- Group A: AIN457 150 mg
- Group B: Placebo

Treatment group for period II:

- Arm A1: AIN457 150 mg
- Arm A2: AIN457 150 mg
- Arm A3: AIN457 300 mg
- Arm B1: AIN457 150 mg
- Arm B2: AIN457 300 mg

The analysis of study treatment data will be based on the safety set for period I, period II and the entire treatment period separately. The number of active and placebo injections will be summarized by treatment group up to Week 8, the number of double blind injections will be summarized by treatment group from Week 8 to Week 24.

Rescue medication

Not applicable.

Duration of exposure

The duration of exposure to study treatment will be summarized by treatment group. In addition, the number and percentage of patients with cumulative exposure levels (e.g. any exposure, ≥ 1 week, ≥ 2 weeks, ≥ 3 weeks, ≥ 4 weeks, ≥ 8 weeks, etc.) will be presented.

Duration of exposure for secukinumab groups will be defined as the time from first dose of study treatment to the time of treatment end for each treatment period. Duration of exposure for the placebo group will be defined as the time from first dose of placebo treatment to the time of treatment end in treatment period 1 and the time from first dose of active treatment to the time of treatment end in treatment period 2.

For patients who discontinue, this will be the patient's last visit in the corresponding treatment period.

Duration of exposure (years) = duration of exposure (days) / 365.25

Duration of exposure (100 subject years) = duration of exposure (years) / 100

The analyses of duration of exposure described above will be done for both the study treatment periods.

Compliance

Compliance will be calculated based on documented study drug administrations and syringe counts and displayed by treatment group.

Compliance is expected to be 100%, unless temporary interruption is needed for safety reasons. Compliance will also be assessed by a Novartis monitor using information provided by the authorized site personnel.

Compliance (%) = 100(total no of injections administered)/(no. of injections prescribed).*

Compliance for entire treatment period will be based on active treatment exposure.

2.4.2 Prior, concomitant and post therapies

Prior and concomitant therapies

Prior and concomitant medications will be summarized in separate tables by treatment group.

Prior medications are defined as treatments taken and stopped prior to first dose of study treatment. Any medication given at least once between the day of first dose of randomized study treatment and the date of the last study visit will be a concomitant medication, including those, which were started pre-baseline and continued into the period where study treatment is administered.

Medications will be presented in alphabetical order, by Anatomical Therapeutic Classification (ATC) codes and grouped by anatomical main group. Tables will show the overall number and percentage of patients receiving at least one treatment of a particular ATC code and at least one treatment in a particular anatomical main group.

Significant prior and concomitant surgeries and procedures will be summarized by primary system organ class and MedDRA preferred term.

The number and percentage of patients receiving prior and concomitant spondyloarthritis therapy will be presented by randomized treatment group as well as the reasons for stopping their therapies (primary lack of efficacy, secondary lack of efficacy, lack of tolerability, other).

Prior or concomitant medication will be identified by comparing recorded or imputed start and end dates of medication taken to the reference start date.

2.5 Analysis of the primary objective

The primary objective is to assess the superiority of secukinumab 150 mg compared to placebo in achieving a spinal pain score < 4 on a 0-10 NRS at Week 8.

2.5.1 Primary endpoint

The primary efficacy endpoint is the proportion of patients with a response of spinal pain NRS score < 4 in secukinumab 150 mg s.c. and placebo at Week 8.

The analysis of the primary variable will be based on the FAS-TP1 patients.

2.5.2 Statistical hypothesis, model, and method of analysis

The null hypothesis to be rejected is that the odds of response at Week 8 are equal in both treatment groups. The corresponding alternative hypothesis is that the odds of response at Week 8 are higher under secukinumab compared to placebo.

Let p_j denote the proportion of responders at Week 8 for treatment group j , $j=0, 1$, where

- 0 corresponds to placebo
- 1 corresponds to secukinumab

In statistical terms, the following hypothesis will be tested:

$H_0: (p_1 / (1 - p_1)) / (p_0 / (1 - p_0)) = 1$ versus $H_A: (p_1 / (1 - p_1)) / (p_0 / (1 - p_0)) \neq 1$

In other words,

H_A : The odds ratio of achieving a response at Week 8 for secukinumab vs. placebo is different from 1.

The primary analyses will be conducted via logistic regression model with treatment, country and the stratification factor of prior exposure to TNF inhibitors (naïve/ inadequate responders to TNF α inhibitors) as factor. The Odds ratio, 95% confidence interval (CI) and p-value will be presented comparing secukinumab 150 mg treatment group to placebo group at Week 8.

The null hypothesis of equal odds will be rejected if the 2-sided p-value from the logistic regression model for the factor “treatment” is < 0.05 ; however, superiority of secukinumab will be claimed only if the direction is correct, i.e. if the odds of response are larger under secukinumab.

Summary statistics will also be reported for each treatment group and by visit. Graphical representation will also be performed.

Grouping of countries: Due to the small number of subjects in some of the countries, the below mentioned countries will be grouped together to perform inferential analysis. The basis of grouping is a similar medical practice and geographical proximity in these countries:

- 1) Ireland & Great Britain
- 2) Italy, Spain & Croatia
- 3) Switzerland & Belgium
- 4) Finland & Sweden
- 5) Lithuania, Latvia & Estonia

If the grouping of countries does not allow proper analysis and if there are any challenges in model convergence, covariate “country” will be excluded from model.

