### 4.1 Inclusion criteria

Patients eligible for inclusion in this study must fulfill all of the following criteria:

1. Patient must be able to understand and communicate with the investigator and comply with the requirements of the study and must provide written, signed and dated informed consent before any study assessment is performed.
2. Male or non-pregnant, non-nursing female patients at least 18 years of age with diagnosis of axSpA (either AS or nr-axSpA) according to ASAS axSpA classification criteria (Appendix 4) to be applied in patients with back pain for at least 3 months and age of onset  $< 45$  years:
  - Sacroiliitis on imaging (see Appendix 6) with  $\geq 1$  SpA feature (see Appendix 4)  
**or**
  - Human Leukocyte Antigen-B27 (HLA-B27) positive with  $\geq 2$  SpA features (see Appendix 4).
3. Active axSpA as assessed by total BASDAI score  $\geq 4$  at Baseline.
4. Spinal pain NRS score  $> 4$  at Baseline.
5. Patients should have been on at least 2 different NSAIDs at the highest recommended dose for at least 4 weeks in total prior to randomization with an inadequate response or failure to respond, or less if therapy had to be withdrawn due to intolerance, toxicity or contraindication.

6. Patients who are regularly taking NSAIDs (including COX-1 or COX-2 inhibitors) as part of their axSpA therapy are required to be on a stable dose for at least 2 weeks before randomization.
7. Patients who have previously been on a TNF $\alpha$  inhibitor will be allowed entry into study after an appropriate wash-out period prior to randomization:
  - 4 weeks for Enbrel® (etanercept) – with a terminal half-life of 102  $\pm$  30 hours (s.c. route)
  - 8 weeks for Remicade® (infliximab) – with a terminal half-life of 8.0-9.5 days (i.v. infusion)
  - 10 weeks for Humira® (adalimumab) – with a terminal half-life of 10-20 days (average 2 weeks) (s.c. route)
  - 10 weeks for Simponi® (golimumab) – with a terminal half-life of 11-14 days
  - 10 weeks for Cimzia® (certolizumab) – with a terminal half-life of 14 days

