### **9.4.4 Sensitivity analyses**

The raw spinal pain NRS scores will be analyzed using a repeated measures analysis of variance (ANOVA) model. The model will include the same factors as the logistic model above plus the baseline score as a covariate.

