2.5.4 Sensitivity analyses

The average spinal pain and raw (total and nocturnal spinal pain separately) NRS scores will be analyzed using a repeated measures analysis of variance (ANOVA) model. The model will include the same factors as the logistic model of primary analysis plus the respective baseline score as a covariate. Analysis visit will be used as repeat factor.

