2.7.2 Statistical hypothesis, model, and method of analysis

The statistical hypothesis for BASDAI score < 4 being tested is that the odds of response at Week 8 are equal in the secukinumab 150 mg treatment group versus placebo group.

Let p_j denote the proportion of responders at Week 8 for treatment group j , $j=0, 1$, where

- 0 corresponds to placebo
- corresponds to secukinumab

In statistical terms, the following hypothesis will be tested:

$H_0: (p_1 / (1-p_1)) / (p_0 / (1-p_0)) = 1$ versus $H_A: (p_1 / (1-p_1)) / (p_0 / (1-p_0)) \neq 1$

In other words,

H_A : The odds ratio of achieving a response at Week 8 for secukinumab vs. placebo is different from 1.

The secondary analyses will be conducted analogous to the primary analyses, i.e., via logistic regression model with treatment, country and the stratification factor of prior exposure to TNF inhibitors (naïve/ inadequate responders to TNF α inhibitors) as factor. The Odds ratio, 95% confidence interval (CI) and p-value will be presented comparing secukinumab 150 mg treatment group to placebo group at Week 8. Confirmatory evidence for the superiority of secukinumab with respect to the secondary endpoint will be claimed only if the 2-sided p-value from the logistic regression model for the factor “treatment” is < 0.05 and if the direction is correct, i.e. if the odds of response are larger under secukinumab and if the superiority of secukinumab with respect to the primary endpoint has already been demonstrated.

Summary statistics will also be reported for each treatment group and by visit. Graphical representation will also be performed.

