5.4 Statistical models

5.4.1 Primary analysis

The null hypothesis to be rejected is that the odds of response at Week 8 are equal in both treatment groups. The corresponding alternative hypothesis is that the odds of response at Week 8 are higher under secukinumab compared to placebo.

The primary analyses will be conducted via logistic regression model with treatment, country and the stratification factor of prior exposure to TNF inhibitors (naïve/ inadequate responders to TNF α inhibitors) as factors. The Odds ratio, 95% confidence interval (CI) and p-value will be presented comparing secukinumab 150 mg treatment group to placebo group at Week 8.

SAS Code for logistic model

```
Proc logistic data=aaa;
Class TRT STRATA / param=glm;
Model AVAL = TRT COUNTRY STRATA;
Lsmeans TRT / diff cl exp;
Ods output diffs=lsm_diff;
Run;
```

In cases where separation is a concern for the primary endpoint at Week 8, e.g. 0% or 100% response in one treatment (sub)group, an exact logistic regression model will be applied to all visits. To ensure convergence, this model will not include any continuous covariates.

```
Proc logistic data=aaa exactonly;
Class TRT STRATA / param=glm;
Model AVAL = TRT COUNTRY STRATA;
Exact TRT / estimate=both;
Ods output exactoddsratio=exactoddsratio;
Run;
```

In addition to that the above analysis will also be performed a sensitivity analysis for raw spinal pain NRS score.

Mixed Model Repeated Measures (MMRM)

The following MMRM (or repeated measures ANOVA) model will be used for analysis of raw (total & nocturnal) and average spinal pain NRS score:

```
proc mixed data=.... order=internal;
where vis_1n in (2, 3, 4, 5, 6, 7);
class trt country strata;
model val_1n = trt bsval_1n country strata/ddfm=kr;
repeated vis_1n / subject=sid1a type=un;
lsmeans trt/ cl diff;
```

run;

If type=Unstructured (un) fails, we will use Compound Symmetry (cs)

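### Neither confirmatory logistic model adjusts for the baseline score, although both endpoints are fixed cut-offs that depend on where the patient started

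*SAP*

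**What the plan says.** - **Primary model, SAP 2.5.2:** "The primary analyses will be conducted via logistic regression model with treatment, country and the stratification factor of prior exposure to TNF inhibitors". The code in SAP 5.4.1 agrees: "Model AVAL = TRT COUNTRY STRATA". Protocol 9.4.2 and the Protocol summary list no baseline score either.
- **Secondary model, SAP 2.7.2:** "The secondary analyses will be conducted analogous to the primary analyses", again "via logistic regression model with treatment, country and the stratification factor of prior exposure to TNF inhibitors".
- **Endpoints:** spinal pain NRS below 4 and BASDAI below 4, both at Week 8.
- **Entry, Protocol 4.1:** "Spinal pain NRS score $> 4$ at Baseline", and total BASDAI of at least 4. SAP 5.5 keeps patients who breach either limit in every analysis set.
- **Where baseline is used:** only in the repeated-measures analysis of the pain scores. Protocol 9.4.4 takes the logistic factors "plus the baseline score as a covariate". SAP 2.5.4 says: "The model will include the same factors as the logistic model of primary analysis plus the respective baseline score as a covariate".
- **Randomization, Protocol 5.3:** stratified by prior TNF inhibitor exposure only.

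No responder analysis, main or sensitivity, adjusts for baseline pain or baseline BASDAI, and no reason is given.

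**The concern.** The pain score is the mean of two 0–10 ratings (Protocol 6.4.1), so it moves in half points and a responder scores 3.5 or less. A patient who enters at 4.5 needs a fall of 4.5 − 3.5 = 1 point; one who enters at 9 needs 9 − 3.5 = 5.5. With an absolute cut-off, baseline should be one of the strongest predictors of response. BASDAI below 4 after entry at 4 or more has the same structure.

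The model spends its degrees of freedom on country instead. Country is not a stratification factor, has to be grouped because some countries are small, and may be dropped if the model does not converge.

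Two things are at stake. Both confirmatory tests give up precision that data already collected would supply. And because nothing in the design balances baseline pain, a chance difference between 264 and 88 patients shifts the unadjusted odds ratio in proportion to the prognostic strength of baseline.

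**Working it through.** **1. The plan's own figure.** Inputs from Protocol 9.8 and SAP section 3: p0 = 0.235, p1 = 0.436, difference d = 0.201, two-sided 5%, 90% power, 3:1 allocation.

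- Pooled rate: (0.235 + 3 × 0.436)/4 = 0.38575.
- Placebo n without continuity correction: [1.960·√((4/3) × 0.38575 × 0.61425) + 1.2816·√(0.235 × 0.765 + 0.436 × 0.564/3)]² / 0.201² = (1.1016 + 0.6557)² / 0.0404 = 76.4.
- With continuity correction: (76.4/4) × [1 + √(1 + 2 × 4/(3 × 76.4 × 0.201))]² = 82.9, so 83 placebo + 249 secukinumab = 332. This matches the plan exactly.

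Without the correction, formula power is 92.3% at 83 + 249 and 93.7% at 88 + 264. The target is met without a baseline term.

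**2. Gain by baseline–Week 8 correlation.** 264 + 88 patients, 3,000 simulated trials per row, response rates held at 43.6% and 23.5%. Assumed, not in the documents: baseline about normal (mean 7, SD 1.6) truncated to above 4; Week 8 SD 2.5. The efficiency ratio is [(1.960 + z(power with)) / (1.960 + z(power without))]². At 0.3, for example, (1.960 + 1.685)²/(1.960 + 1.580)² = 13.29/12.53 = 1.06.

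| Correlation | Power without | Power with | Efficiency ratio |
|---|---|---|---|
| 0.2 | 93.4% | 94.0% | 1.03 |
| 0.3 | 94.3% | 95.4% | 1.06 |
| 0.4 | 93.9% | 95.8% | 1.11 |
| 0.5 | 93.7% | 96.5% | 1.17 |

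On 352 patients, ratios of 1.06 and 1.17 correspond to about 352 × 0.06 = 21 and 352 × 0.17 = 60 extra patients. A separate run under the same assumptions gave 94.2% to 94.9% at 0.3 (ratio 1.05) and 93.4% to 96.8% at 0.5 (ratio 1.18).

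**3. Gain by odds ratio per baseline point.** Model: logit P(response) = arm intercept + ln(odds ratio per point) × baseline, with intercepts set to give 23.5% and 43.6%. Assumed baseline: normal (mean 7, SD 1.5) in half points, cut to above 4 and at most 10. 83 + 249 patients, 3,000 trials per row.

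| Odds ratio per point | Power without | Power with | Efficiency ratio | Mean treatment odds ratio, without / with |
|---|---|---|---|---|
| 0.8 | 92.2% | 93.3% | 1.02 | 2.58 / 2.63 |
| 0.7 | 91.8% | 92.8% | 1.04 | 2.55 / 2.67 |
| 0.6 | 91.3% | 93.9% | 1.09 | 2.54 / 2.78 |
| 0.5 | 92.0% | 95.2% | 1.16 | 2.56 / 3.00 |
| 0.4 | 91.7% | 96.5% | 1.25 | 2.57 / 3.31 |

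At 88 + 264, power rises from 94.0% to 95.7% (0.6 per point) and from 93.1% to 95.9% (0.5 per point).

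**4. Type I error.** With no treatment effect, rejection was 4.6% without and 4.8% with baseline (0.7 per point), and 3.9% and 4.0% (0.5 per point). Omitting baseline does not inflate it.

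**5. Chance imbalance.** Same baseline assumption as step 3, 264 + 88 patients, 4,000 trials per row. The standard error of the difference in baseline means is 1.32 × √(1/88 + 1/264) = 0.16 point. In about 15% of trials the secukinumab arm starts more than 0.16 point worse. Power in those trials:

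| Odds ratio per point | Power without | Power with |
|---|---|---|
| 0.7 | 90% | 94% |
| 0.6 | 87% | 96% |
| 0.5 | 85% | 96% |

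At 0.6 per point, the median unadjusted odds ratio is about 2.2 in these trials and about 2.85 in the mirror case. The adjusted estimate stays near 2.7 to 2.8.

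The simulations omit country and TNF stratum. Monte Carlo error is about 0.5 percentage point in the power figures of step 3 and larger in the subsets of step 5.

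**The case against.** The strongest reply is that nothing is broken. The unadjusted test holds its level under randomization and the trial meets its 90% target without the covariate. At weak correlations the gain is close to simulation noise: 0.6 point at 0.2, while the column without baseline itself varies by 0.9 point between rows. Every gain depends on a prognostic strength that the documents do not give. A chance baseline difference is sampling error that the confidence interval already covers, and baseline scores will be tabulated by arm (SAP 2.3.2). All of this is correct, and it is why the point is a recommended improvement and not an error.

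Other objections carry less weight:

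- **A baseline-adjusted pain analysis already exists.** It models scores, not response. As coded in SAP 5.4.1 it has no visit term and asks only for overall treatment means, so it gives no Week 8 contrast. It does not cover BASDAI.
- **The odds ratio becomes conditional on baseline.** True, and with a strong baseline effect it moves from about 2.55 to as much as 3.3. But the planned odds ratio is already conditional on country and TNF stratum.
- **The exact-logistic fallback bars such a term:** "To ensure convergence, this model will not include any continuous covariates". That clause applies only under separation, so one sentence stating that baseline is dropped there resolves it.
- **The secondary gain is not computed.** This stands. The documents give no BASDAI response rates, so the argument there rests on the shared structure of the endpoint.

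**Conclusion.** The concern holds. Both confirmatory models omit the baseline value of the score that defines response, while the plan uses it as a covariate in a supporting analysis of the same pain data. This is a loss of efficiency and of robustness to chance imbalance. It is not bias on average, type I error inflation or a missed power target.

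For the primary endpoint the size is about 1 to 3 percentage points of power at correlations of 0.3 to 0.5, equal to about 6% to 17% more patients. The gain is smaller at 0.2, and larger in the minority of trials where secukinumab starts with worse pain. These figures rest on the assumed baseline distribution and prognostic strength. That harder-to-reach cut-offs make response less likely follows from the endpoint itself. The change should be made.

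**What to change.** Before unblinding:

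1. Add baseline average spinal pain NRS, as a continuous covariate, to the primary logistic model in Protocol 9.4.2 and SAP 2.5.2 and 5.4.1. Add baseline BASDAI to the secondary model in SAP 2.7.2.
2. State that the Screening value is used when the Baseline value is missing. Both scores are collected at Visit 1 (Protocol Table 6-1), and this agrees with the definition in SAP 2.1.1 of baseline as the last measurement before first dose. It matters because SAP 5.5 keeps patients with a missing baseline pain score (OTH03), whom a complete-case logistic fit would otherwise drop.
3. State that the baseline term is left out if the exact model is needed.
4. State that the reported odds ratio is conditional on baseline as well as on country and TNF stratum.
5. Keep the current model without baseline as a supportive analysis.

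If the sponsor will not change the primary model, the minimum is to prespecify the baseline-adjusted logistic model as a sensitivity analysis for both endpoints.

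The cost is a few lines of text and code and no new data. If the protocol is not amended, SAP section 4, which now reports no changes to the protocol-specified analyses, must record it. The price in interpretation is an odds ratio that may lie further from 1 than the one implied by the two response rates, so the observed proportions should be reported beside it.
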